#### 7.2. Participant Accountability

The number of subjects enrolled, the number randomized who received at least one dose of study drug, the number discontinuing prior to Week 96 and the reason for withdrawal will be summarized by treatment assigned and overall.

A detailed listing of subject status, including screen failures will be created. This listing will show informed consent date, final study status, Study Day 1, and completion or withdrawal date, and for withdrawals, the reason for withdrawal. For screen failures, the primary reason for screen failure will be shown.

# 7.3. Demographic and Baseline Characteristics

The Safety Analysis Set's demographic characteristics will summarize age (in years, truncated to the year of age at baseline) as a quantitative variable by treatment arm and overall, and as counts and percent by treatment arm and overall, for the following categories: 10 to < 14, and 14 to <18 years.

Sex will be summarized as counts and percent for each treatment arm and overall.

Ethnicity (Latino/Not Latino/Not reported due to confidentiality regulations) will be summarized as counts and percent for each treatment arm and overall.

Race will be summarized by counts and percentage into American Indian or Alaska Native, Asian, Black or African American, Native Hawaiian or other Pacific Islander, White, Not reported due to confidentiality regulations, and Other. Other values will be listed but not further categorized. Baseline height (cm) and weight (kg) will be presented with summary statistics by treatment group and overall.

Summaries of baseline disease characteristics (MS disease history, e.g., time since the first MS symptom, time since MS diagnosis, the number of relapses in the past 12 mon, 2 years, the timing of the last relapse prior to enrollment and the will be presented by treatment group for the ITT Population. Medical history and MS Treatment history will be also summarized.

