## 9.2. Randomization and Registration of Subjects

Subjects will be registered and randomized at Baseline (Day 1), after all baseline and screening assessments have been completed and after the Investigator has verified that the subjects are eligible per criteria in Sections 8.1 and 8.2. No subject may begin treatment prior to assignment of a unique identification number (registration) and randomization. Any subject identification numbers that are assigned will not be reused even if the subject does not receive treatment.

Subjects will be randomized in a 1:2:2 ratio to receive BG00012:BIIB017:placebo. Subjects will be stratified by age (10 to  $\leq$ 14 years of age and 15 to 17 years of age) and by site.

Refer to the Study Reference Guide for details on registration and randomization.

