#### Additional Objectives and Endpoints

# 2.2. Study Design

This was a randomized, multicenter, double-blind, and double-dummy placebo-controlled three arm parallel group study to evaluate the efficacy and safety of BG00012 and BIIB017 in pediatric subjects with RRMS.

Approximately 260 subjects aged 10 to 17 years (inclusive) with a diagnosis of RRMS as defined by the revised consensus definition for pediatric MS (Krupp LB, 2013), (Polman CH, 2011) were to be enrolled at approximately 50 sites globally. Eligible subjects were randomized within 6 weeks of screening. At least 25% of subjects were to be no more than 14 years of age. Subjects were stratified by age (10 to ≤ 14 years of age and 15 to 17 years of age) and by site. Subjects were randomized in a 1:2:2 ratio to treatment with placebo, BG00012, BIIB017, respectively. See the Study Activities schedule below for details on study visits. Visits in Week 2 and Week 6 were conducted in-person (optional) or telephonic. Subjects randomized to BG00012 received a starting dose of 120 mg BID orally (twice daily) for 7 days followed by a maintenance dose of 240 mg BID orally. Subjects randomized to BIIB017 were titrated to the target dose of 125 mg: 63 mg on Day 1, 94 mg at Week 2, and 125 mg at Week 4. Once subjects reached the 125 mg target dose, they continued with BIIB017 125 mg subcutaneously (SC) administered every two weeks for the remainder of the study. To ensure blinding across the treatment groups all subjects received BG00012 (or placebo) administered orally BID and BIIB017 (or placebo) administered SC every two weeks.

An Unscheduled Relapse Visit occurred as required to conduct neurological and evaluations within 72 hours of any new neurological symptoms that could indicate the onset of a clinical relapse. Confirmed relapses were treated at the treating neurologist's discretion with intravenous methylprednisolone (IVMP) at any time from Baseline to Week 100. Such treatment did not affect the subject's eligibility to continue in the study. The primary endpoint of the study was the TTFR: therefore, subjects were required to remain on the assigned blinded treatment until they experience their first protocol-defined relapse or disability progression.

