# 3. Early termination of study due to sponsor's decision

The BLAST study was put on hold in 2021 due to low recruitment. After notification of all interested parties (investigators, IRBs, ethics committees, and regulatory agencies), BLAST was canceled by Biogen with the consent of the FDA. At the time the study was put on hold, 16 subjects had been screened and 11 subjects had been enrolled.

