#### 5.4. Stratification Factors and Subgroup Variables

#### 5.4.1. Stratification Factors

The study was stratified on age and site. Age was the subject age at Baseline (Study Day 1).

- Age
  - Baseline age 10 to less than or equal to 14 years
  - Baseline age greater than 14 years.
- Site—approximately 50 sites will be used world-wide.

Recruitment was used to ensure that at least 25% of subjects were in the 10 to less than or equal to 14 years age group. All analyses that fit a statistical model were to include the age stratification. Analyses were not to be stratified by site.

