#### 6. List of Planned Study Analyses

As noted above, BLAST was terminated early due to the severely limited subject enrollment and progress in the study. As a result, the data collected are insufficient to support the original study objectives. The protocol study plan is changed as reflected in this document to briefly summarize the baseline characteristics and safety data by treatment group and overall. The data summaries are descriptive in nature: comparison among the study treatment groups is inappropriate. Drug efficacy and PRO data will not be summarized but will be provided in listings.

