#### 6.2. Primary Analysis

The primary analysis will be performed after the data base is locked. The primary analysis will consist of two parts: Subject summaries and Safety Analysis. The Subject summaries will provide a complete listing of all collected data for each subject. The Safety Analysis will consist of AE summaries.

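### Should the age rows of the demographic table be recut because they place 14-year-olds differently from the randomization strata?

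*SAP*

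**What the plan says.** SAP section 7.3 summarizes age in the Safety set in two ways, by arm and overall. It is treated as a quantitative variable, truncated to completed years at baseline, and as counts and percentages "for the following categories: 10 to < 14, and 14 to <18 years".

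The randomization strata are cut one year higher. Protocol section 9.2 runs the younger stratum from 10 up to and including 14; the older end of the definition reads "14 years of age and 15 to 17 years of age) and by site". SAP section 2.2 gives the same strata and adds a recruitment minimum: "At least 25% of subjects were to be no more than 14 years of age". SAP section 5.4.1 defines the strata as "Baseline age 10 to less than or equal to 14 years" and "Baseline age greater than 14 years".

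The setting has changed since the protocol was written. SAP section 3 records that, when the trial was put on hold, "16 subjects had been screened and 11 subjects had been enrolled". SAP section 6 keeps only descriptive summaries of baseline and safety data and states that "comparison among the study treatment groups is inappropriate". SAP section 6.2 promises a "complete listing of all collected data for each subject".

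**The concern.** When a trial stratifies by a two-level age factor and its baseline table shows a two-level age split, a reader will tend to assume that they are the same split. Here they are not. Because SAP section 7.3 truncates age, everyone from the 14th birthday to the day before the 15th counts as 14 and falls in the older row, although randomized in the younger stratum. The table therefore cannot be used directly to see the balance of the stratification factor or to check the 25% minimum.

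The baseline table is also one of the few summaries left once the efficacy analyses were dropped, which makes an inconsistency in it more visible. In a full-size trial with age-stratified models, two age definitions in one report could lead to a misread subgroup or a model coded on the wrong cut.

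A related doubt concerns SAP section 5.4.1, which does not say that age is in completed years. Taken alone and on exact age, it would put a child aged 14 and a half in the older stratum.

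**Working it through.** No figure in the plan (sample size, power, event count or significance level) depends on the age rows, so there is none to reproduce. The check maps ages to groups and then traces where the groups are used.

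**1. Inputs.** Eligible ages are 10 to 17 inclusive at consent (Protocol section 8.1). The strata come from Protocol section 9.2 and SAP section 2.2, the display rows from SAP section 7.3, and the 11 enrolled subjects from SAP section 3.

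**2. Mapping of completed years.**

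| Completed age | Randomization stratum | SAP 7.3 row | Same side of the cut? |
|---|---|---|---|
| 10, 11, 12, 13 | 10 to ≤14 | 10 to <14 | yes |
| 14 | 10 to ≤14 | 14 to <18 | no |
| 15, 16, 17 | 15 to 17 | 14 to <18 | yes |

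Matches: 4 + 3 = 7 of 8 ages. Mismatches: 1 of 8, age 14.

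**3. Direction and size.** Let n14 be the number of subjects aged 14. For ages 10 to 17:

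- younger row = younger stratum − n14
- older row = older stratum + n14

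The younger row can equal or understate the younger stratum but never exceed it. The documents do not give n14; with 11 enrolled it lies between 0 and 11. If the table holds all 11 (an assumption, since the size of the Safety set is not stated), each 14-year-old moves the overall percentage by 1/11 = 9.1 points; with n14 = 0 nothing moves. The 9.1 points reflect how few subjects there are. They do not measure harm.

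**4. Where the age groups are used.**

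- SAP section 5.4.1 requires the age strata only in analyses that fit a statistical model. Sections 7.5.1 and 7.5.2 drop the primary and secondary efficacy analyses, so no model remains.
- SAP section 5.4.2 plans no subgroup analyses.
- SAP section 7.6.1 summarizes adverse events by treatment and overall, not by age.
- SAP section 7.3 also gives the quantitative summary of age, which does not depend on the cut.

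The age rows feed no other output.

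**5. The wording of SAP section 5.4.1.** Take a child aged 14.5.

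- On exact age, section 5.4.1 gives the older stratum, while the strata in SAP section 2.2 give neither group, because 14.5 is above 14 and below 15.
- On completed years the age is 14, and both sections give the younger stratum.

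Only completed years makes the two sections agree and leaves nobody aged 14 without a stratum. It is also the scale that section 7.3 states. An analyst would settle this without new text.

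**6. The 25% minimum.** It governed recruitment of about 260 subjects: 0.25 × 260 = 65 in the younger group. With 11 enrolled and the trial cancelled, no planned output tests it.

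**The case for a change.** The best case for a change is that it would cost almost nothing: a short edit to SAP section 7.3, perhaps a clarifying phrase in section 5.4.1, and one format change in the table program. Rows of 10 to ≤14 and 15 to 17 would put all eight ages on the matching side. The SAP gives no reason for its different cut, and with so few subjects a single 14-year-old can visibly change the percentages within an arm. Being able to rebuild the strata limits the harm but does not make the two definitions agree.

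Part of this stands. The inconsistency is in the current SAP text, it looks unintended, and matching rows would be tidier. A programmer who used the strata for the display would be doing nothing wrong.

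The rest carries little weight. The SAP does not call the section 7.3 rows strata, and each row states its own limits, so the table is accurate as labelled. The missing justification is not a lapse either: SAP section 4 describes departures from the protocol's analysis, and the protocol's statistical section asks for summary statistics and frequency distributions without fixing age categories for a demographic table. There was no protocol display to depart from. The effect within an arm depends on a count that is unknown and may be zero, and it would bear on a comparison between arms that the SAP already calls inappropriate.

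One side point: eligibility age is fixed at consent and the table uses baseline age, so a subject who turned 18 during screening would fall in neither row. The counts would then fall short of the total, and an analyst would notice and deal with it.

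**Conclusion.** The observation is correct, and no change is needed. One completed-year age out of eight is displayed on the other side of the cut from its stratum. The effect is confined to a correctly labelled pair of rows in one descriptive table. Nobody's stratum changes, and no estimate, test or safety result depends on the rows, so recutting them would alter nothing that the trial does or can conclude.

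This rests on three things in the documents: the analysis stays descriptive as SAP section 6 sets out, no age-stratified model or subgroup analysis is reinstated, and the listings in SAP section 6.2 show each subject's age so that the strata can be rebuilt for the 11 enrolled. If a stratified analysis were ever revived, the strata of Protocol section 9.2 would apply, because SAP section 5.4.1 already ties any fitted model to the stratification factor and not to the section 7.3 rows.

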#### 7.4. Protocol Deviations

Major and minor protocol deviations identified in the study will be listed.

#### 7.5. Study Treatment Exposure and Concomitant Medications

Duration of study treatment and time on study will be summarized by treatment received for the Safety Population. Compliance until the last dose will also be summarized by treatment received for the Safety Population.

The number of doses taken will be computed per visit as

Doses taken = Doses dispensed – Doses returned.

The number of doses taken will be listed by visit. Compliance will be computed per subject as

Compliance = (Doses Taken – Doses Expected)/Doses Expected.

See Section 5 for the definitions of treatment duration and time on study.

A Concomitant therapy was defined as any therapy that was taken on or after the day of the first dose of study drug. This includes therapies that start prior to the initiation of the first dosing if their use continues on or after the date of the first dose. All concomitant medications were coded using the World Health Organization (WHO) medication dictionary (September 2021). All concomitant non-drug therapies were coded using the Medical Dictionary for Regulatory Affairs (MedDRA) Version 24.1.

Numbers and percentages of subjects taking concomitant medications and non-drug therapies will be summarized by treatment group.

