#### 11.1.1. BG00012

BG00012 will be taken orally. Subjects will take 1 capsule orally at a dose of 120 mg BID for the first 7 days and 2 capsules orally at a dose of 240 mg BID thereafter.

Subjects will be instructed to swallow each BG00012 capsule whole and not chewed. The capsule and its contents are not to be crushed, divided, dissolved, sucked, or chewed since the enteric-coating of the microtablets in the capsule helps to prevent irritant effects on the stomach. If unable to swallow the capsule, the capsule may be opened and the contents mixed with food *immediately* prior to consumption.

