## **11.2.** Modification of Dose and/or Treatment Schedule

### 11.2.1. Dose Reduction

Dose reduction will be allowed only for subjects who are unable to tolerate BG00012 *due to flushing and/or GI disturbances* (dose reductions will not be allowed for abnormal laboratory values). Subjects who do not tolerate BG00012 will reduce their dose by taking one 120 mg capsule BID for up to 4 weeks. Within 4 weeks at the reduced dose, subjects will resume taking 2 capsules BID. If the subject is still unable to tolerate BG00012, the subject must discontinue BG00012 as described in Section 10.1. Any subject who prematurely discontinues dosing with BG00012 may remain in the study and continue protocol-scheduled tests and assessments.

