## 11.4. Compliance

Compliance with treatment dosing is to be monitored and recorded by site staff. Compliance will be monitored by capsule count and syringe or auto-injector pen count conducted by study personnel at protocol-scheduled visits.

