## 12.2. BIIB017

BIIB017 is supplied as a liquid in an auto-injector pen to deliver 0.5 mL of 0.25 mg/mL (125  $\mu$ g dose) of 20 kDa mPEG-O-2-methylpropionaldehyde-modified human IFN  $\beta$ -1a in 20 mM acetic acid/sodium acetate buffer pH 4.8, 150 mM arginine hydrochloride, and 0.005% polysorbate 20.

BIIB017 is also supplied as a liquid in a prefilled-syringe (PFS) for titration dosing to deliver 0.5 mL of 0.13 mg/mL (63  $\mu$ g dose) or 0.19 mg/mL (94  $\mu$ g dose) of 20 kDa mPEG-O-2-methylpropionaldehyde-modified human IFN  $\beta$ -1a in 20 mM acetic acid/sodium acetate buffer pH 4.8, 150 mM arginine hydrochloride, and 0.005% polysorbate 20.

The label will include conditions for storage, kit number, and other pertinent information in accordance with local regulations such as Sponsor, expiration date, and a caution statement. BIIB017 should not be used after the expiration date unless a written notification of an expiration date extension is provided by Biogen.

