## 5.2. Study Treatment

This study was a double-blinded, double-dummy, placebo-controlled trial. To maintain the blind all subjects received a placebo for the treatment they are not assigned.

**BG00012** (Tecfidera) was to be taken orally at a dose of 120 mg BID for the first 7 days (1 capsule daily), and at 240 mg BID thereafter (2 capsules daily). The BG00012 treatment group will receive a placebo injection of BIIB017 vehicle every two weeks.

**BIIB017** (Plegridy) was to be administered SC at a dose of 125 μg every two weeks for 96 weeks. BIIB012 subjects will be titrated to the target dose on the following schedule: 63 μg BIIB017 on Day 1, 94 μg at Week 2, and 125 μg every other week thereafter for the duration of the trial. BIIB017 subjects will receive daily placebo capsule(s) on the same schedule as BG00012 subjects.

**Placebo** subjects were to receive a SC injection of the BIIB017 vehicle every 2 weeks and daily placebo capsules according to the titration regimen for the BG00012 group.

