#### 7. Statistical Methods for Planned Analyses

## 7.1. General Principles

The only planned analysis for this study is the final report. This study design is structured to minimize subject exposure to placebo, and because each active arm functions as a distinct study, multiplicity adjustments are unnecessary.

This is a double-blind, double-dummy study. The blind may be broken in case of a medical emergency if the treating physician needs to know the assigned treatment. Once unblinded, the subject will no longer receive study treatment. The investigator must document the cause for the unblinding in the source documents and make efforts to avoid unblinding other study personnel, limiting treatment information to those involved in the medical emergency.

Subjects will be instructed not to take a dose of study drug within 4 hours of a clinic visit to prevent drug-induced symptoms from being observed by study personnel and risk their unblinding. After the final clinical study report is completed, Biogen will inform the clinical investigators who may inform subjects about the treatment they received, if this does not jeopardize ongoing related studies.

Otherwise, all blinding will remain in place until the data base is locked.

Summary statistics for quantitative variables will consist of the mean, standard deviation, number of non-missing observations, minimum, the median, and the maximum. All quantitative data will be summarized with these statistics classified by treatment arm and visit unless otherwise noted below. Summary statistics for categorical data will consist of the frequency count and the percentage with respect to a study-relevant base (usually the number of subjects at-risk).

Among the demographic data, age, baseline height, and baseline weight will be summarized as quantitative variables. Race, ethnicity, sex, and will be summarized as categorical variables. No graphics are planned for the demographic data.

Missing dates will be handled as shown in Table 1 below.

Table 1. Date imputation rules for AE and Concomitant Medication.

	Missing	Condition	Imputed Value			
Start date (AE, concomitant medication)	Day	The event started in the same year and month as Study Day 1 (or treatment period start date)	Study Day 1 (or treatment period start date)			
		Otherwise	01			
	Day and month	The event started in the same year as Study Day 1 (or treatment period start date)	Study Day 1 (or treatment period start date)			
		Otherwise	01JAN			

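### The compliance formula in SAP 7.5 equals taken/expected minus 1, so full adherence prints as 0 and 80% adherence as −0.20

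*SAP*

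**What the plan says.** SAP 7.5 counts doses taken at each visit as those dispensed less those returned. It then gives the per-subject measure: "Compliance = (Doses Taken – Doses Expected)/Doses Expected". The output is mandatory: "Compliance until the last dose will also be summarized by treatment received for the Safety Population". SAP 7.1 fixes the statistics: "Summary statistics for quantitative variables will consist of the mean, standard deviation, number of non-missing observations, minimum, the median, and the maximum".

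The protocol offers no competing formula. Section 11.4 says only that "Compliance will be monitored by capsule count and syringe or auto-injector pen count", made by study personnel at scheduled visits.

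On dosing units, protocol 12.2 is clear for the injection: "BIIB017 is supplied as a liquid in an auto-injector pen to deliver 0.5 mL of 0.25 mg/mL", which is one 125 µg dose per pen, and the titration syringes likewise each deliver one dose. For the capsules, SAP 5.2 describes BG00012 "at a dose of 120 mg BID for the first 7 days (1 capsule daily), and at 240 mg BID thereafter (2 capsules daily"), while protocol 11.1.1 has "2 capsules orally at a dose of 240 mg BID thereafter".

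**The concern.** The numerator subtracts the expected doses, so the quantity measures how far a subject departs from full dosing. The name attached to it tells the reader something else. A subject who took every dose gets 0, and a subject who took none gets −1.00. The value most open to misreading is 0: a median compliance of 0.00 could be read as no drug taken when it means complete adherence.

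Efficacy is confined to listings in this SAP, so exposure and compliance are among the few quantities still summarized, and they give context for the adverse event tables. A programmer must either print values that do not match their label or depart from a final SAP without a record.

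One wording gap goes with this. All subjects receive both capsules and injections, and the SAP does not say whether an oral dose is one capsule or one twice-daily intake, or whether the two routes are computed separately.

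**Working it through.** Neither document states a compliance value, so there is no figure to reproduce. The check is algebraic.

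**Inputs.** T = doses taken and E = doses expected, both from SAP 7.5. Write a = T/E for true adherence.

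**Formula as written.** (T − E)/E = T/E − 1 = a − 1. The result does not depend on E, so neither treatment duration nor route changes it.

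| True adherence a | SAP 7.5 prints | 100 × T/E |
|---|---|---|
| 1.05 | 0.05 | 105% |
| 1.00 | 0.00 | 100% |
| 0.90 | −0.10 | 90% |
| 0.80 | −0.20 | 80% |
| 0.50 | −0.50 | 50% |
| 0.00 | −1.00 | 0% |

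**Effect on the summary table.** Subtracting 1 from every value lowers the mean, median, minimum and maximum by exactly 1. It leaves the SD and n as they were. As an illustration, take five assumed subjects at 1.00, 0.95, 0.90, 0.80 and 0.50:

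| Statistic | T/E | SAP 7.5 |
|---|---|---|
| Mean | 4.15/5 = 0.83 | −0.17 |
| Median | 0.90 | −0.10 |
| Minimum | 0.50 | −0.50 |
| Maximum | 1.00 | 0.00 |
| SD | √(0.158/4) = 0.199 | 0.199 |

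**Does another section correct it?** No. Protocol 11.4 names the counts but gives no formula. SAP 7.1 lists the statistics without any conversion. SAP 5.5 defines two analysis populations, and neither uses a compliance threshold that would show a different scale was meant.

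**Capsule counts (separate point).** Protocol 12.1 gives 120 mg per capsule. By arithmetic, 120 mg twice daily is 2 × 1 = 2 capsules a day and 240 mg twice daily is 2 × 2 = 4 a day. SAP 5.2 prints 1 and 2 a day beside the same twice-daily doses, a factor of 2 apart. Protocol 11.2.1 also counts capsules per intake ("taking one 120 mg capsule BID for up to 4 weeks"), although that sentence is the dose-reduction rule and not the standard schedule. SAP 7.5 does not tie expected doses to the SAP 5.2 counts, so this is not shown to affect the compliance figure.

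**The case against.** The strongest case against is that nothing has been miscalculated. The SAP prints its definition openly, a relative deviation is a legitimate statistic, and under that definition every summary value is right. On this view the fault is one of labeling, and changing the label would cure it as well as changing the formula. That is fair as to the remedy. It does not remove the defect, because the output is called compliance and nothing tells the reader that it is a deviation.

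The second argument is that the consequence is close to nil, and most of this stands. Adding 1 recovers the ratio, and the ordering of subjects is unchanged. Doses taken are also listed by visit. SAP section 3 reports 11 subjects enrolled at the time of the hold, and section 6 calls comparison among the groups inappropriate. Negative values would alert most readers, although a 0 might not. SAP section 4 provides for listings in place of tables when data are limited. The visible text there concerns safety data and part of the sentence is missing, so it may not cover compliance. A per-subject compliance listing built on this formula would in any case show the same values.

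The third argument is that the capsule counts and the oral unit are different matters. That is correct, and they are kept separate here. They neither cause nor enlarge the formula error.

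**Conclusion.** The concern holds. As written, SAP 7.5 reports a − 1 under a label that means a. The shift is a fixed −1 (100 percentage points) in the four location statistics, with the SD and n correct. The algebra needs no assumption. Calling the values too low assumes only that compliance carries its usual meaning of taken over expected.

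The importance is minor. The error is confined to a descriptive exposure summary in a terminated study. No analysis population depends on compliance, no subgroup analyses are planned, and no efficacy or adverse event output uses the formula. The listing of doses taken does not use it either, though it shares the unstated oral unit.

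**What to change.** Replace the definition in SAP 7.5 with: compliance (%) = 100 × doses taken / doses expected, over the period to the last dose that the section already specifies. Compute it separately for capsules and for syringes or pens, as protocol 11.4 counts them. Keep taken and expected in the same unit, and state whether the oral unit is a capsule or an intake. Full adherence then prints as 100%. If the sponsor prefers the present quantity, rename it as relative deviation from expected doses wherever it appears.

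As a separate item, reconcile the capsule counts in SAP 5.2 with protocol 11.1.1, 11.2.1 and 12.1 before expected doses are derived.

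The cost is one formula line, one clause on unit and route, and a one-line program change. No new data are needed, since the protocol already has the counts made. Because the SAP is final at Version 1.0, the correction needs a new SAP version or a documented change in the study report.
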